## **11. MANAGEMENT AND REPORTING OF ADVERSE EVENTS/ADVERSE REACTIONS**

### **11.1 DEFINITIONS OF ADVERSE EVENTS**

#### Adverse event

An adverse event (AE) is defined as any untoward medical occurrence in a patient or clinical investigation subject administered a medicinal product and which does not necessarily have a causal relationship with this treatment. An adverse event can therefore be any unfavourable and unintended sign (e.g. an abnormal laboratory finding), symptom, or disease temporally associated with the use of a medicinal product, whether or not considered related to the medicinal product.

#### Adverse reaction

An adverse reaction is defined as a response to a medicinal product which is noxious and unintended. Response in this context means that a causal relationship between a medicinal product and an adverse event is at least a reasonable possibility. Adverse reactions may arise from use of the product within or outside the terms of the marketing authorisation or from occupational exposure. Conditions of use outside the marketing authorization include off-label use, overdose, misuse, abuse and medication errors.

#### Serious adverse event

A serious adverse event is defined as any AE which

- results in death,
- is life-threatening,
- requires in-patient hospitalization, or
- prolongation of existing hospitalisation,
- results in persistent or significant disability or incapacity, or
- is a congenital anomaly/birth defect

Life-threatening in this context refers to a reaction in which the patient was at risk of death at the time of the reaction; it does not refer to a reaction that hypothetically might have caused death if more severe.

Medical and scientific judgement should be exercised in deciding whether other situations should be considered serious reactions, such as important medical events that might not be immediately life threatening or result in death or hospitalisation but might jeopardise the patient or might require intervention to prevent one of the other outcomes listed above.

Examples of such events are intensive treatment in an emergency room or at home for allergic bronchospasm, blood dyscrasias or convulsions that do not result in hospitalisation or development of dependency or abuse. Any suspected transmission via a medicinal product of an infectious agent is also considered a serious adverse reaction.

**Adverse Event of Special Interest (AESI)**

The term Adverse Event of Special Interest (AESI) relates to any specific AE that has been identified at the project level as being of particular concern for prospective safety monitoring and safety assessment within this study, e.g. the potential for AEs based on knowledge from other compounds in the same class.

No AESIs have been defined for this study.

**11.2 ADVERSE EVENT AND SERIOUS ADVERSE EVENT COLLECTION AND REPORTING**

The investigator shall maintain and keep detailed records of all AEs in their patient files.

**Collection of AEs**

The study design is of non-interventional nature and the study is conducted within the conditions of the approved marketing authorisation. Sufficient data from controlled interventional trials are available to support the evidence on the safety and efficacy of the studied BI drug. For this reason the following AE collection and reporting requirements have been defined.

The following must be collected by the investigator in the eCRF from signing the informed consent onwards until the end of the study:

- all (serious and non-serious) adverse drug reaction(ADRs), related to Spiolto® Respimat®,
- all AEs with fatal outcome (serious adverse events),

*Note\*: For all patients on these data must be recorded on the AE pages in the eCRF. The separate NIS (S)AE form must in addition be used and forwarded to the local Pharmacovigilance as indicated in the form.*

All ADRs , including those persisting after study completion must be followed up until they are resolved, have been sufficiently characterized, or no further information can be obtained.

The investigator carefully assesses whether an AE constitutes an ADR using the information below.

**Causal relationship of adverse event**

The definition of an adverse reaction implies at least a reasonable possibility of a causal relationship between a suspected medicinal product and an adverse event. An adverse reaction, in contrast to an adverse event, is characterised by the fact that a causal relationship between a medicinal product and an occurrence is suspected.

Medical judgment should be used to determine the relationship, considering all relevant factors, including pattern of reaction, temporal relationship, de-challenge or re-challenge, confounding factors such as concomitant medication, concomitant diseases and relevant history.

Arguments that may suggest a **reasonable causal relationship** could be:

- The event is **consistent with the known pharmacology** of the drug
- The event is known to be caused by or **attributed to the drug class**.
- **A plausible time to onset of the event** relative to the time of drug exposure.
- Evidence that the **event is reproducible** when the drug is re-introduced
- **No medically sound alternative etiologies** that could explain the event (e.g. pre-existing or concomitant diseases, or co-medications).
- The event is typically **drug-related and infrequent in the general population** not exposed to drugs (e.g. Stevens-Johnson syndrome).
- An indication of dose-response (i.e. greater effect size if the dose is increased, smaller effect size if dose is diminished).

Arguments that may suggest that there is **no reasonable possibility of a causal relationship** could be:

- No plausible time to onset of the event relative to the time of drug exposure is evident (e.g. pre-treatment cases, diagnosis of cancer or chronic disease within days/weeks of drug administration; an allergic reaction weeks after discontinuation of the drug concerned)
- Continuation of the event despite the withdrawal of the medication, taking into account the pharmacological properties of the compound (e.g. after 5 half-lives). Of note, this criterion may not be applicable to events whose time course is prolonged despite removing the original trigger.
- Additional arguments amongst those stated before, like alternative explanation (e.g. situations where other drugs or underlying diseases appear to provide a more likely explanation for the observed event than the drug concerned).
- Disappearance of the event even though the study drug treatment continues or remains unchanged.

#### Intensity of adverse event

The intensity of the AE should be judged based on the following:

Mild: Awareness of sign(s) or symptom(s) which is/are easily tolerated

Moderate: Enough discomfort to cause interference with usual activity

Severe: Incapacitating or causing inability to work or to perform usual activities

#### Pregnancy:

In rare cases, pregnancy might occur in a study. Once a subject has been enrolled into the study, after having taken Spiolto® Respimat®, the investigator must report any drug exposure during pregnancy, which occurred in a female subject or in a partner to a male subject to the Sponsor by means of Part A of the Pregnancy Monitoring Form. The outcome of the pregnancy associated with the drug exposure during pregnancy must be followed up and reported by means of Part B of the Pregnancy Monitoring Form.

In the absence of a reportable AE, only the Pregnancy Monitoring Form must be completed, otherwise the NIS (S)AE form is to be completed and forwarded to the local Pharmacovigilance point of contact for each country within respective timelines.

#### Expedited Reporting of AEs and Drug Exposure During Pregnancy

The following must be reported by the investigator on the NIS AE form from signing the informed consent onwards until the end of the study:

| Type of Report  | Timeline                    |
|---|-----------------------------|
| All serious ADRs associated with Spiolto® Respimat®                  | immediately within 24 hours |
| All AEs with fatal outcome in patients exposed to Spiolto® Respimat® | immediately within 24 hours |
| All non-serious ADRs associated with Spiolto® Respimat®              | 7 calendar days             |
| All pregnancy monitoring forms associated with Spiolto® Respimat®    | 7 calendar days             |

The same timelines apply if follow-up information becomes available for the respective events. In specific occasions the Investigator could inform the Sponsor upfront via telephone. This does not replace the requirement to complete and fax/email the NIS (S)AE form.

Information required

For each reportable adverse event, the investigator should provide the information requested on the appropriate eCRF pages and the (S)AE NIS form.

Reporting of related Adverse Events associated with any other BI drug

The investigator is encouraged to report all adverse events related to any BI drug other than the Spiolto® Respimat® according to the local regulatory requirements for spontaneous AE reporting at the investigator's discretion by using the locally established routes and AE report forms. The term AE includes drug exposure during pregnancy, and, regardless of whether an AE occurred or not, any abuse, off-label use, misuse, medication error, occupational exposure, lack of effect, and unexpected benefit.

### **11.3 REPORTING TO HEALTH AUTHORITIES**

Adverse event reporting to regulatory agencies will be done by the MAH according to local and international regulatory requirements.

## **12. PLANS FOR DISSEMINATING AND COMMUNICATING STUDY RESULTS**

Results of this non-interventional study will be disclosed on [encepp.eu](http://encepp.eu) and [clinicaltrials.gov](http://clinicaltrials.gov) and a study specific publication plan will be developed to describe planned publications.

The rights of the investigator and of the sponsor with regard to publication of the results of this study are described in the investigator contract. As a general rule, no study results should be published prior to finalisation of the Study Report.

## **ANNEX 1. LIST OF STAND-ALONE DOCUMENTS**

The stand-alone documents for this non-interventional study are:

- Informed Consent Form
- CCQ Questionnaire
- Physician's Global Evaluation (PGE)\*
- Breathlessness Scale (mMRC)
- Statistical Analysis Plan (SAP)
- Data Management Plan (DMP)
- Serious Adverse Event Report in Non-Interventional Studies - (S)AE NIS Form
- Pregnancy Monitoring Form

All of the above documents will be archived in the Trial Master File in its original English master version.

*\* to be completed directly within the eCRF*

## **ANNEX 2. ENCEPP CHECKLIST FOR STUDY PROTOCOLS**

*Not applicable*

## **ANNEX 3. ADDITIONAL INFORMATION**

### **1. Physician's Global Evaluation (PGE)\***

*\* to be completed directly within the eCRF*

General condition of the patient at the initial examination (Visit 1)

Please mark with a cross as applicable

|                            |                            |                            |                            |                            |                            |                            |                            |
|----------------------------|----------------------------|----------------------------|----------------------------|----------------------------|----------------------------|----------------------------|----------------------------|
| Poor                       | Satisfactory               | Good                       | Excellent                  |                            |                            |                            |                            |
|  1 |  2 |  3 |  4 |  5 |  6 |  7 |  8 |

General condition of the patient after 4 to 6 weeks of treatment (Visit 2)

Please mark with a cross as applicable

|                            |                            |                            |                            |                            |                            |                            |                            |
|----------------------------|----------------------------|----------------------------|----------------------------|----------------------------|----------------------------|----------------------------|----------------------------|
| Poor                       | Satisfactory               | Good                       | Excellent                  |                            |                            |                            |                            |
|  1 |  2 |  3 |  4 |  5 |  6 |  7 |  8 |

## **2. Patient Satisfaction Questionnaire**

**Please choose the number which best describes your satisfaction with Spiolto® Respimat®.**

**What is your overall satisfaction with the Spiolto® Respimat® treatment?**

|  |   |   |  |   |  |   |
|--|---|---|--|---|--|---|
| 1
very dissatisfied
 | 2
dissatisfied
 | 3
rather
dissatisfied
 | 4
neither satisfied
nor dissatisfied
 | 5
rather satisfied
 | 6
satisfied
 | 7
very satisfied
 |
|--|---|---|--|---|--|---|

**How satisfied are you with inhaling from the Respimat® device?**

|  |   |   |  |   |  |   |
|--|---|---|--|---|--|---|
| 1
very dissatisfied
 | 2
dissatisfied
 | 3
rather
dissatisfied
 | 4
neither satisfied
nor dissatisfied
 | 5
rather satisfied
 | 6
satisfied
 | 7
very satisfied
 |
|--|---|---|--|---|--|---|

**How satisfied are you with the handling of the Respimat® inhalation device?**

|  |   |   |  |   |  |   |
|--|---|---|--|---|--|---|
| 1
very dissatisfied
 | 2
dissatisfied
 | 3
rather
dissatisfied
 | 4
neither satisfied
nor dissatisfied
 | 5
rather satisfied
 | 6
satisfied
 | 7
very satisfied
 |
|--|---|---|--|---|--|---|

### 3. Clinical COPD Questionnaire

| CLINICAL COPD QUESTIONNAIRE  |                    |                       |                  |                    |              |                    |                                  |
|---|--------------------|-----------------------|------------------|--------------------|--------------|--------------------|----------------------------------|
| Please circle the number of the response that best describes how you have been feeling during the past week .
(Only one response for each question). |                    |                       |                  |                    |              |                    |                                  |
| On average, during the past week , how often did you feel:   | never              | hardly ever           | a few times      | several times      | many times   | a great many times | almost all the time              |
| 1. Short of breath at rest ?   | 0                  | 1                     | 2                | 3                  | 4            | 5                  | 6                                |
| 2. Short of breath doing physical activities ?   | 0                  | 1                     | 2                | 3                  | 4            | 5                  | 6                                |
| 3. Concerned about getting a cold or your breathing getting worse?   | 0                  | 1                     | 2                | 3                  | 4            | 5                  | 6                                |
| 4. Depressed (down) because of your breathing problems?  | 0                  | 1                     | 2                | 3                  | 4            | 5                  | 6                                |
| In general, during the past week , how much of the time:   |                    |                       |                  |                    |              |                    |                                  |
| 5. Did you cough ?   | 0                  | 1                     | 2                | 3                  | 4            | 5                  | 6                                |
| 6. Did you produce phlegm ?  | 0                  | 1                     | 2                | 3                  | 4            | 5                  | 6                                |

**4. Modified Medical Research Council (mMRC) Questionnaire for Assessing the Severity of Breathlessness**

**Please circle the number which best describes your grade of breathlessness.**

I only get breathless with strenuous exercise. 0

I get short of breath when hurrying on the level or walking up a slight hill. 1

I walk slower than people of the same age on the level because of breathlessness, or have to stop for breath when walking at my own pace on the level. 2

I stop for breath after walking about 100 meters or after a few minutes on level. 3

I am too breathless to leave the house or I am breathless when dressing or undressing. 4

## **2. LIST OF ABBREVIATIONS**

Term	Definition / description
AE	Adverse event
BI	Boehringer Ingelheim Pharma GmbH&Co. KG
CCQ	Clinical COPD Questionnaire
CR	Complete Response
COPD	Chronic obstructive lung disease
GOLD	Global Initiative for Chronic Obstructive Lung Disease
LABA	Long-acting beta2-adrenoceptor agonist
LAMA	Long-acting anticholinergic bronchodilator
Max	Maximum
MedDRA	Medical Dictionary for Drug Regulatory Activities
Min	Minimum
mMRC	Modified Medical Research Council Scale
NIS	Non-interventional study
PGE	Physician's global Evaluation
SAE	Serious Adverse event
TEAE	Treatment-emergent AE
TSAP	Trial Statistical Analysis Plan

### **3. INTRODUCTION**

As per ICH E9, the purpose of this document is to provide a more technical and detailed elaboration of the principal features of the analysis described in the protocol, and to include detailed procedures for executing the statistical analysis of the primary and secondary variables and other data.

This TSAP assumes familiarity with the Clinical Trial Protocol (CTP), including Protocol Amendments. In particular, the TSAP is based on the planned analysis specification as written in CTP Section 9.7 "Data Analysis". Therefore, TSAP readers may consult the CTP for more background information on the study, e.g., on study objectives, study design and population, treatments, definition of measurements and variables, planning of sample size, randomization.

SAS® Version 9.4 or higher will be used for all analyses.

#### **4. CHANGES IN THE PLANNED ANALYSIS OF THE STUDY**

- In addition to the protocol, subgroup analyses will be performed for all secondary endpoints, i.e. for changes from baseline in CCQ scores (symptom, functional state (CCQ-4), mental state and total scale), patient's satisfaction and willingness to continue treatment as well as PGE
- New analyses set, which is not mentioned in the protocol (Details are displayed in TSAP Section 6.3):
  - Full analysis set (FAS)

## **5. ENDPOINT(S)**

### **5.1 PRIMARY ENDPOINT(S)**

The primary endpoint of the presented study is “therapeutic success” at visit 2 i.e. approximately 6 weeks after starting treatment, defined as 0.4-point decrease in the total CCQ score between visit 1 and visit 2.

### **5.2 SECONDARY ENDPOINT(S)**

- Absolute changes in CCQ scores (symptom, functional state (CCQ-4), mental state and total scale) from visit 1 to visit 2
- General condition of the patient, evaluated by the physician (PGE score) at visit 1 and visit 2
- Patient satisfaction with Spiolto® Respimat® at visit 2
- Patients’ willingness to continue with Spiolto® Respimat® at visit 2

### **5.4 OTHER VARIABLE(S)**

Other variables will be baseline characteristics and patient’s characteristics such as age, gender, height and weight. Additionally information about concomitant medication, diseases, therapy data, further therapies and comorbidities will be collected as well as about smoking status, exacerbation history, mMRC and GOLD group.

## **6. GENERAL ANALYSIS DEFINITIONS**

### **6.1 TREATMENT(S)**

In the presented study, treatment with Spiolto® Respimat® will be according to product information.

### **6.2 IMPORTANT PROTOCOL VIOLATIONS**

Table 6.2: 1 defines the different categories of important protocol violations (PVs). The final column describes which PVs will be used to exclude subjects from the different patient analysis sets.

Table 6.2: 1 Important protocol violations

Category/Code		Description	Requirements	Excluded from
A		Entrance criteria not met		
	A1.1	Inclusion criterion 2 (Female or male patients >=40 years of age)	Not met as specified in the protocol	None
	A1.2	Inclusion criterion 3 (Patients diagnosed with COPD and requiring a combination of two long-acting bronchodilators according to Spiolto® Respimat® SmPC, GOLD COPD strategy document 2018 (GOLD COPD groups B to D) and local COPD guidelines)	Not met as specified in the protocol	None
	A2.1	Exclusion criterion 1 (Patients with contraindications according to Spiolto® Respimat® SmPC)	Met as specified in the protocol	None
	A2.2	Exclusion criterion 2 (Patients already on a LABA/LAMA or LABA/LAMA/ICS combination (free and fixed dose) in the last 6 weeks before study entry)	Met as specified in the protocol	None
	A2.3	Exclusion criterion 3 (Patients continuing LABA/ICS treatment after study enrolment)	Met as specified in the protocol	None
	A2.4	Exclusion criterion 4 (Current participation in any clinical trial or any other non-interventional study of a drug or device)	Met as specified in the protocol	None
	A2.5	Exclusion criterion 5 (Pregnancy or lactation)	Met as specified in the protocol	None
B		Informed consent		
	B1	Informed consent not available/not done (Inclusion criterion 1)	IC 01 not met as specified in the protocol or informed consent date missing	All

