| Study design:  | Open-label observational: all included COPD patients are receiving treatment with Spiolto® Respimat® for approximately 6 weeks, which is the average time between two medical consultations.  |                                 |   |
| Population:  | COPD patients requiring a combination therapy of two long-acting bronchodilators (LAMA + LABA) according to approved SmPC and GOLD guidelines, COPD GOLD groups B to D (Version 2018).  |                                 |   |

|   |   |                                 |   |
|---|---|---------------------------------|---|
| Name of company:
Boehringer Ingelheim                                 |   |                                 |   |
| Name of finished medicinal product:
Spiolto® Respimat®                |   |                                 |   |
| Name of active ingredient:
R03AL06
Tiotropium bromide + Olodaterol |   |                                 |   |
| Protocol date:
26 March 2018  | Study number:
1237-0072   | Version/Revision:
1.0 | Version/Revision date:
Not applicable |
| Variables:   | 

- Patient demographics (age, gender, height & weight)

- Concomitant diseases / Comorbidities

- Concomitant medication

- General condition of patient based on Physician's Global Evaluation PGE)

- Smoking history

- Exacerbation history

- Breathlessness based on mMRC score

- CCQ and the CCQ symptom, mental state and functional state domain scores

- Patient satisfaction with Spiolto® Respimat®

- Safety; ADR (serious and non-serious), fatal AEs, pregnancies

- GOLD patient groups (B, C, D)

- GOLD spirometric classification (1-4), if available

 |                                 |   |
| Data sources:  | 
To be completed by the physician:
 

- Patient demographics

- Patient medical files

- Physician's Global Evaluation (PGE) at visit 1 and visit 2

- Document patient's willingness to continue treatment

 
To be completed by the patient:
 

- mMRC breathlessness scale at visit 1

- Health and functional status by CCQ questionnaire at visit 1 and 2

- Patient satisfaction survey at Visit 2

   |                                 |   |

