### **6.3 PATIENT SETS ANALYZED**

**Full analysis set (FAS):** All screened patients with informed consent, date of registration (date of creation of screening form in the eCRF), and at least one documented administration of Spiolto® Respimat® and available total CCQ score at visit 1 and visit 2.

**Treated set (TS):** All screened patients with informed consent, date of registration (date of creation of screening form in the eCRF), and at least one documented administration of Spiolto® Respimat®.

Table 6.3: 1 Patient sets analyzed

Class of endpoint	Patient set	
	TS	FAS
Primary and secondary endpoints		X
Safety endpoints	X	
Demographic/baseline	X	

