### **7.3 PRIMARY ENDPOINT**

For the primary endpoint, the percentage of patients with therapeutic success will be presented together with the 95% confidence interval, whereupon therapeutic success is defined as 0.4-point decrease in CCQ score from visit 1 to visit 2. The number and percentage of patients with and without therapeutic success will be calculated for the whole FAS set and the above mentioned subgroups.

For comparison of subgroups,  $\chi^2$ -Test or Fisher's Exact test, if  $\chi^2$ -Test is not valid, will be used and p-values will be interpreted nominally. Additionally, 95% confidence intervals for the percentage of patients with therapy success will be calculated for each subgroup analyzed.

The total CCQ score ranges from 0 to 6. A higher score is indicative of worse status. If a patient fills in two answers on one question the data will be considered as missing. Missing values will not be imputed, one answer in the subscales “symptom” and “CCQ-4” might be missing, respectively, in order to calculate the total score. The total CCQ score and the corresponding subscales are calculated as followed, in case that at least the number of required answers is available:

Scale	Items	Items required	Scoring (For details see www.ccq.nl )
Symptom	1; 2; 5; 6	3	$\frac{\text{Sum of answered questions}}{\text{Number of answered questions}}$
Functional state (CCQ-4)	7-10	3	$\frac{\text{Sum of answered questions}}{\text{Number of answered questions}}$
Mental state	3; 4	2	$\frac{\text{Item 3 + 4}}{2}$
Total CCQ score	All subscales must be calculable		$\frac{(\text{Symptom} + \text{Functional state}) * 4 + (\text{Mental state}) * 2}{10}$

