## 10. HISTORY TABLE

Table 10: 1 History table

Version	Date (DD-MMM- YY)	Author	Sections changed	Brief description of change
Draft v0.1	18-JUL-2018		None	This is the first Draft-Version of TSAP without any modification
Draft v0.2	31-AUG-2018		6.2	Violation of A1.2 does not lead to exclusion of any analysis set
			6.3	Definition of analysis sets changed, i.e. "diagnosis of COPD in whom treatment with two long acting bronchodilators is indicated" no longer necessary to be analyzed
			6.4	Definition of "maintenance naïve" added
Draft v0.3	03-DEC-2018		4, 6.2, 6.3	Comments added, that have to be discussed
Draft v0.4	17-JAN-2019		4., 6.4	Subgroups adapted
Draft v0.5	22-FEB-2019		4., 6.4	Definition of treatment naïve added
Final 1.0	27-FEB-2019		6.3	Date of registration specified
Final 2.0	19-JUL-2019		7.7	Corrected "NCI-CTC grade" to "severity"

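### Should the SAP add a success rate without important protocol violators, and a summary of the time between visits?

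*SAP*

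**What the plan says.** SAP section 6.2 introduces its table of important protocol violations with the statement "The final column describes which PVs will be used to exclude subjects from the different patient analysis sets". That column reads *None* for all seven entrance criteria (A1.1, A1.2 and A2.1 to A2.5) and *All* only for B1, missing informed consent. Three of the codes bear on the primary endpoint:

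- **A1.2**: diagnosis, indication or GOLD group not met. The protocol abstract describes the population as "COPD patients requiring a combination therapy of two long-acting bronchodilators (LAMA + LABA") in GOLD groups B to D.
- **A2.2**: "Patients already on a LABA/LAMA or LABA/LAMA/ICS combination (free and fixed dose) in the last 6 weeks before study entry".
- **A2.3**: LABA/ICS continued after enrolment.

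For A1.2 the SAP history table records the decision in draft v0.2: "Violation of A1.2 does not lead to exclusion of any analysis set".

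SAP section 6.3 defines two sets. Besides consent and a registration date, the full analysis set (FAS) requires "at least one documented administration of Spiolto® Respimat® and available total CCQ score at visit 1 and visit 2"; the treated set drops the CCQ condition. Neither has an eligibility condition. Under SAP section 7.3 the numbers with and without success "will be calculated for the whole FAS set and the above mentioned subgroups", with a 95% confidence interval for each subgroup.

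On timing, the protocol abstract has patients treated "for approximately 6 weeks, which is the average time between two medical consultations". SAP section 6.7 repeats the approximate six weeks without a day range, and SAP section 7.6 on extent of exposure is marked as not applicable.

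**The concern.** A violation labelled important would normally have some consequence in the analysis. Here the label has no visible use for the primary endpoint. The study has no control group, so the change between visits carries the whole result, and each of the three codes alters what that change means. An A1.2 patient lies outside the stated population. For an A2.2 patient, visit 1 is not a baseline before dual bronchodilation. An A2.3 patient takes Spiolto together with a treatment that the protocol's exclusion criteria rule out alongside it.

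Two further points seem to add to this. One documented administration is enough for the FAS, so a patient who stopped early but returned for visit 2 counts like any other. And nothing visible shows how long after visit 1 the second CCQ was completed. At stake is whether a rate reported to about ±1.5 points could depend on patients or visit times outside the study's own description, without the reader being able to tell.

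**Working it through.** **Inputs.** Protocol section 9.5 gives 50% success, 4050 evaluable patients, limits of 48.5% and 51.5%, and 10% drop-out. The documents give neither the share of violators nor their success rate, so both are assumed below.

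**The plan's own figures.** Half-width = 1.96 × √(0.5 × 0.5 / 4050) = 0.0154, so the limits are 48.46% and 51.54%, which agrees with the protocol to rounding. Enrolment: 4050 / 0.9 = 4500, as stated.

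**Effect of leaving violators out.** Let f be their share and d the difference in success between the other patients and the violators.

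- Shift in the overall rate = f × d.
- Difference needed for a shift of one planned half-width = 1.54 / f.
- New half-width = 1.96 × √(0.25 / n kept).
- Half-width of the shift itself, since the two sets overlap = 1.96 × f × √(0.25 / n kept + 0.25 / n removed).

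| Assumed share f | Kept / removed | Shift if d = 15 points | d needed for 1.54 points | New half-width | Half-width of the shift |
|---|---|---|---|---|---|
| 2% | 3969 / 81 | 0.3 | 77.0 | 1.56 | 0.22 |
| 5% | 3848 / 202 | 0.75 | 30.8 | 1.58 | 0.35 |
| 10% | 3645 / 405 | 1.5 | 15.4 | 1.62 | 0.51 |
| 20% | 3240 / 810 | 3.0 | 7.7 | 1.72 | 0.77 |

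The shift can go either way. At 2% it is negligible, and at 5% it needs an implausibly large difference to matter. It is comparable with the sampling error only from about 10% upward, combined with a difference of about 15 points at that share. Nothing in the documents points to such a share.

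**Early stoppers.** A success rate in stoppers would be imprecise if they are few: 1.96 × √(0.25 / 40) = 15.5 points with 40 patients (about 1%) and 1.96 × √(0.25 / 202) = 6.9 points with 202 (5%).

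**Is the FAS a departure from the protocol?** Protocol section 9.7 takes everyone with at least one dose and leaves out of the primary analysis anyone lacking a CCQ score at either visit. For the primary endpoint that is the FAS in substance. The protocol sets no eligibility condition for analysis, so the removal of the diagnosis and indication condition in draft v0.2 brought the SAP back into line with it.

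**What is already planned.** Protocol section 9.7 lists respiratory treatment before and during the study, GOLD groups, reasons for ending treatment, and continuation or discontinuation. SAP section 3 rests on that section. These summaries should show how common prior dual therapy, continued LABA/ICS and stopping were, though not the success rates in those patients. The history table also records, for sections 4 and 6.4, "Definition of treatment naïve added", and a maintenance-naïve definition for 6.4. Subgroups built on these would receive a success rate and interval under section 7.3 and may partly cover A2.2.

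**Timing.** Extent of exposure concerns drug intake, so marking section 7.6 as not applicable says nothing about visit dates. SAP section 7 provides general summaries for continuous variables. The documents contain nothing from which an effect of the interval on the success rate could be computed.

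**The case for a change.** The strongest case for a change is that it would cost almost nothing. The codes exist, and prior therapy, concomitant medication, GOLD group and discontinuation are collected. Even with 10% of patients removed the interval widens only from ±1.54 to ±1.62 points, and the shift would be known to about ±0.5. The A1.2 decision dates from 31 August 2018, after the planned start of data collection in Q2 2018, which is a reason to show the narrower population as well. The naïve subgroups would not clearly isolate A1.2 or A2.3.

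Part of this stands. No visible analysis gives the rate without violators, and the visible text has no summary of the visit interval. But the contents list of the SAP passes over sections 5.3, 6.4 and 7.5, which are not in the public text, so one cannot say that the SAP lacks these analyses. The late date carries little weight, because the protocol, dated 26 March 2018, already called for all treated patients. That visit dates are recorded is also an assumption, since the protocol's visit table does not list them. What remains is that a supportive table would be cheap and sometimes informative. That makes it an option, not a correction.

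**Conclusion.** No change to the plan follows. Keeping violators in the FAS is the as-treated choice that protocol section 9.7 makes, and it suits a descriptive study which, by protocol section 9.9, wants a broad population in everyday practice. The handling is set out in advance code by code, and no bias has been shown. On assumed shares of 2% to 5%, a 15-point difference in success moves the rate by 0.3 to 0.75 points against a planned half-width of 1.54. Only at an assumed 10% or more, with differences of about 15 points or (at 20%) 7.7 points, would the shift reach that half-width, and even that is not a decision threshold here, since no hypothesis is tested. The conclusion would weaken if violators proved common and very different. The planned therapy and GOLD summaries should reveal whether they are common, and an analyst could then add the supportive rate from codes already defined.

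An approximate visit 2 is a fair trade-off when visits follow routine consultations. Two wording differences are clerical and should be reconciled without touching the analysis. The physician's evaluation form in protocol Annex 3 puts visit 2 at 4 to 6 weeks, against about 6 weeks elsewhere. Code A2.2 also names LABA/LAMA/ICS, which the matching exclusion criterion in protocol section 9.2.2 does not.
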